**ADAPTATION OF COMMUNITY REINFORCEMENT APPROACH FOR
THE TREATMENT OF DRUG ADDICTION**

[name]

74-FSS/PHDPSY/F-18

[name]

Associate Professor (supervisor)

Department of Psychology

Faculty of Social Sciences

International Islamic University Islamabad

July 10, 2024

Statistical Analysis Plan

The collected data for this clinical trial was analyzed using SPSS 25 version. Important statistical analysis includes independent sample t-test, paired sample t-tests and one way ANOVA was used. Following are the defining parameters.

Independent sample t-test

Independent sample t-test was used to understand the efficacy of the treatment program between control and experimental groups.

Paired sample t-test

Paired sample t-test was used to elaborate the differences between the level of assessment. In order to assess the differences on pre and post assessment of interventions based on SCL-90 (scale of comorbidity).

One way ANOVA

One way ANOVA was used to understand the differences between pre assessment, post assessment and follow up to draw conclusion about the recovery of the participants which is measured by ARQ (Addiction recovery questionnaire).

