## **Objectives:**

- To investigate whether IICRA has the better efficacy in treating substance dependence along with comorbidities than the indoor conventional treatment for substance dependence.
- To adapt the IICRA treatment strategy grounded in Pakistani culture and religious values for the treatment of drug addicts in Pakistan.

- To determine whether IICRA treatment is more effective in treating poly drug addicts and drug addicts with or without comorbidities.
- To determine whether IICRA treatment is more effective for those addicts who were treated for one or more treatment previously as compare to those having first treatment.

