### **Research Method and Design:**

A randomized control trial was used as research method on indoor residential patients and guidelines of good clinical practices were followed (Guideline, 2001). The sample size for this clinical trial was 60 in total (30 for control group and 30 for treatment group) in order to maintain this number, the sample size was extended to 34 for each group in order to get adequate retention of the sample. The retention number of sample was 68 at the time of pre assessment and closed at 59 at the time of last follow up assessment. All participants who were admitted for treatment of SUD with or without comorbid mental disorders were recruited for research. Intervention was administered after the 21 days of detoxification. For recruitment and randomization, it was not applicable to control extraneous variables in a single facility so two sites were selected for this purpose. Selection of sites were based on minimizing extraneous variables by selecting identical residential treatment sites. One site such as Islamabad Rehab Clinic (IRC) was willing to give permission for implementation of IICRA based intervention. Hence, IRC was selected for recruiting treatment group.

Second site was considered for recruiting control group where they were giving traditional treatment in residential setting based on disease model. The site is named as Hayat Rehab Clinic (HRC). The permission for conducting research and recruiting participants were sought out from the authorities. Traditional treatment was termed as treatment as usual which includes detoxification of drugs and duration of detoxification from acute withdrawal consisted on 21 days,

During these early days focus was on adjustment to residential treatment along with hygiene and routine related compliance. Afterwards, the focus was on general counselling for drug addiction prevention, twelve steps program, habit formation based on seven habits for highly effective people and life skills training which is mainly delivered through group classes and lectures. Patients' individual sessions are also scheduled with psychologists once weekly, the focus of these individual sessions is to maximize the interaction with family through relationship building and relapse prevention skills. Duration of residential treatment is between 90-120 days.

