The treatment group received interventions based on Islamically Integrated CRA (IICRA). These sessions were divided into daily goals including counseling related to hygiene, physical activities, psychotherapy of mental disorders and drug addiction related management. After discharge from residential treatment, they were followed up for six months to check the effectiveness of IICRA in the context of relapse and recovery from SUD as well as from comorbidities. These six months follow up was consist of further three follow up sessions; first session was conducted on the discharge date from the facility, second was on fifth month and third was on sixth month following discharge.

Sample in the present study for clinical trial was based on those diagnosed individuals who were hospitalized in rehab for the treatment of SUD. Age of the sample was varying from 16 years to 60 years, where 24% individuals were from late adolescence, 39% from early adulthood and finally 37% were from middle adulthood. The chronicity of disease in the sample varies 78% of them were abusing substance between from one year to 10 years and 22% were abusing more than 10 years. Similarly, the rate of relapse or number of treatments within sample was computed as 54% individuals were hospitalized first time and 46% were hospitalized two and more than two times. Additionally, the type of substance abuse was also varying cross the

sample which included cannabis, alcohol, pills, heroin, Ice and multiple substance abuse (Alcohol, cannabis and prescribed substances) as well. The gender was mainly male in sample which was 98% and only one participant was female in the sample. Moreover, 75% individuals of the sample were diagnosed with SUDs and 25% were also having comorbid mental illness. Hence, the representativeness of the sample was limited to clinical population diagnosed with SUDs as well as comorbidities with SUDs.

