Secondly, the professionals who were providing treatment were not aware of the allocation of the individual in control and treatment group as well as the recruited individuals for the clinical trial. They were responsible for conducting sessions and recording those sessions through treatment forms as well as monitoring the goals whether desired goal is achieved or not. They were also given the treatment protocol schedule for effective treatment adherence. Additionally, panel assessments were planned at both sites for reviewing and addressing treatment related issues faced by professionals as well as the achievement of desired goals of the treatment. These panel assessments were carried out by weekly to ensure the engagement of the patients, adherence and fidelity to the treatment protocols. This committee was comprised of four professionals having experience in the treatment planning and execution with the minimum educational level of MS in Clinical Psychology.

Moreover, for the purpose of comparability of results and to control the extraneous variables, two treatment sites were selected for clinical trial. Both sites were equal in terms of organizational structure which includes residential treatment facility for mental health, same geographical region with outdoor areas, hierarchy of professionals, daily routine of the patients, psychiatrist consultation, outdoor and indoor activities of the patients and length of residential

treatment. The professionals engaged in the clinical trial has similar qualification and experience at both facilities.

During this clinical trial, 28 out of 34 participants were retained in control group and successfully completed the duration of clinical trial. Three participants had withdrawn the treatment after 40 days of hospitalization and one individual passed away after discharge from rehab. Remaining two participants did not continue the follow up sessions.

Similarly, in experimental group 31 participants out of 34 had successfully completed the Treatment duration for clinical trial. Two participants had withdrawn the treatment after a month of admission and one participant did not continue after the discharge from the facility.

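### The SAP in hand is worded after follow-up closed, ties its between-arm t-test to no scale or visit and describes no error-rate control, so a single nominal p<0.05 is not confirmatory.

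*SAP*

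**What the plan says.** **Timing.** Protocol and SAP are both dated July 10, 2024. The SAP's opening paragraph states "The collected data for this clinical trial was analyzed using SPSS 25 version". Under Research Method and Design, the protocol reports that the sample "closed at 59 at the time of last follow up assessment". It also gives retention by arm: "28 out of 34 participants were retained in control group", and "in experimental group 31 participants out of 34 had successfully completed the" treatment.

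**Tests.** The SAP lists three:
- an independent-samples t-test comparing the control and experimental groups for efficacy, with no scale and no visit named;
- a paired t-test on the SCL-90, before versus after the intervention;
- a one-way ANOVA on the ARQ across the assessment occasions.

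It states no primary endpoint, primary time point, significance level, sidedness or multiplicity rule.

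**Visits.** In the protocol's account of follow-up, the "first session was conducted on the discharge date from the facility, second was on fifth month and third was on sixth month following discharge".

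**Subgroups.** The protocol's Objectives include "To determine whether IICRA treatment is more effective in treating poly drug addicts and drug addicts with or without comorbidities", and a further objective contrasts previously treated patients with those in their first treatment. The SAP describes no analysis for either.

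**The concern.** A p-value below 0.05 supports a confirmatory claim when the comparison was fixed before the outcomes were known, or when the error rate over all eligible comparisons is controlled. The documents show neither. Because the efficacy t-test has no named scale or visit, any of several between-arm results could be presented as the planned proof of the protocol's first objective, which is superiority over conventional treatment.

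The paired t-test and the ANOVA, as described, compare occasions and not arms. Improvement over time in residential patients would be expected under either treatment, so a significant result from either test could be mistaken for evidence that IICRA is better.

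**Working it through.** **1. Reproduce the plan's own figure.** The protocol's attrition counts give:
- control: 34 − 3 − 1 − 2 = 28;
- experimental: 34 − 2 − 1 = 31;
- total: 28 + 31 = 59, which agrees with the stated count at last follow-up.

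The numbers at the final visit were therefore known when these documents were written.

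**2. Count the between-arm tests that the wording allows.** The SAP gives no count, so each is a reading:
- *Three:* SCL-90 after treatment; ARQ after treatment and at one follow-up.
- *Four:* as above, with ARQ at two follow-ups.
- *Six:* both scales at all three follow-up sessions (2 × 3 = 6).

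The three- and four-test readings take the discharge session as the post-treatment assessment, which the documents do not state. The six-test reading assumes that both scales were taken at every session, which they do not state either.

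**3. Upper guide, independent tests.** Chance of at least one false positive = 1 − (1 − 0.05)^k:
- k = 3: 1 − 0.95³ = 14.3%
- k = 4: 1 − 0.95⁴ = 18.5%
- k = 6: 1 − 0.95⁶ = 26.5%

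**4. Allow for correlation.** The tests share patients, so the true figures are lower. Trials were simulated under no effect with 28 versus 31 patients. Assumed inputs, none given in the documents: two-sided 0.05 per test, between-scale correlation 0.3 to 0.7, between-visit correlation 0.4 to 0.8.

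| Between-arm tests | At least one p<0.05, either direction | At least one p<0.05 favouring IICRA |
|---|---|---|
| 1 | about 5% | nominal 2.5% |
| 3 | 11-14% | 5-7% |
| 4 | 12-18% | 6-9% |
| 6 | 16-24% | 8-12% |

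A separate calculation with equicorrelated normal test statistics gives 12.6% for three tests and 21.0% for six at correlation 0.5, consistent with the table. Stronger correlation lowers the figures, but none of the combinations tried falls to 5%.

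**5. First Holm threshold.** With m tests, the smallest p-value is compared with 0.05/m: 0.0167 for three, 0.0125 for four and 0.0083 for six.

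**The case against.** **Timing is inferred.** The past tense shows when this text was written, not when the tests were chosen. The last-visit date is not given and an earlier dated plan may exist. This stands as a qualification: producing such a plan would answer the timing point. It would answer the multiplicity point only if it also named the scale and visit or a rule for error control.

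**Six tests may be too many.** The SAP links the SCL-90 to two occasions only, so three or four between-arm tests is a fair reading. This stands, and is why a range is given. Even three tests roughly double the error rate or more.

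**A two-sided count overstates the risk of a false efficacy claim.** This also stands. About half of the false positives would favour control. The relevant comparison is then 5-12% against 2.5%, which is still at least a twofold inflation.

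**Stronger readings to avoid.** A reader might infer that the SAP runs unadjusted tests across subgroups, and might repeat the six contrasts in both halves of the three subgroup factors to reach 42 tests. The SAP contains no subgroup test. The protocol poses the subgroup questions, and the SAP gives them neither a test nor an adjustment. That is a gap, but a 42-test analysis is not in either document. A reader might also infer that the documents claim confirmatory significance at 0.05. They state no significance level and do not use that term.

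**Site.** Each arm was recruited at its own clinic, so no adjusted p-value can separate IICRA from site. This is true, but it is a separate limitation and gives no reason to leave the multiplicity undisclosed.

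**Conclusion.** The point holds in this form. The SAP in hand is dated and worded after follow-up had closed, leaves the efficacy comparison open as to scale and visit, and describes no error-rate control. Under the stated assumptions, the chance of at least one false-positive between-arm result is about 11-24% across the plausible counts, or about 5-12% counting only results that favour IICRA. A single nominal p<0.05 therefore cannot be read as confirmatory evidence of efficacy.

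The size rests on an assumed two-sided 0.05 per test, an assumed count of three to six tests and assumed correlations. The direction does not depend on the exact values. It is not established that the tests were chosen because of the results; the documents only fail to exclude it.

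**What to change.** 1. State in the SAP that it was finalised after data collection, or supply the earlier dated plan.
2. Define the family as every whole-sample between-arm contrast: each scale at each post-baseline session at which it was measured. Report all of them with estimate and 95% CI.
3. Show Holm-adjusted p-values across that complete family, labelled post hoc. Holm limits selective reading of the results, but chosen now it cannot restore prespecification. Nor can naming a primary test now.
4. Label subgroup comparisons, paired t-tests and time-only ANOVA results as exploratory, and do not offer them as evidence that IICRA is superior.

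**Cost.** SAP and report wording plus a short re-tabulation; no new data. The adjusted p-values will be less favourable. With 28 versus 31 patients, the standardised difference detectable with 80% power is (z for 1 − α/2 + z for 0.80) × √(1/28 + 1/31). That is 0.73 at 0.05, 0.84 at 0.0167 (three tests) and 0.91 at 0.0083 (six tests). The adjusted figures apply to the strictest Holm step.

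### The one between-arm test the SAP lists gives no scale, time point, score type or use of the pre-assessment, so it does not fix how the comparative objective is answered

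*SAP*

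**What the plan says.** The first item under Objectives in the protocol is "To investigate whether IICRA has the better efficacy in treating substance dependence along with comorbidities than the indoor conventional treatment". Under Research Method and Design, participants are to be "followed up for six months to check the effectiveness of IICRA in the context of relapse and recovery from SUD as well as from comorbidities". Recovery from both dependence and comorbidity is therefore an outcome on which the arms are to be compared.

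The SAP describes three tests:

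- **Independent t-test:** "Independent sample t-test was used to understand the efficacy of the treatment program between control and experimental groups". This is the whole description.
- **Paired t-test:** "In order to assess the differences on pre and post assessment of interventions based on SCL-90 (scale of comorbidity").
- **One-way ANOVA:** "differences between pre assessment, post assessment and follow up to draw conclusion about the recovery of the participants", with ARQ as the measure. No group factor is mentioned.

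The protocol names neither scale and describes no analysis, so it does not fill in the SAP.

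On recruitment, Research Method and Design says of the first clinic: "Hence, IRC was selected for recruiting treatment group". Of the other it says: "Second site was considered for recruiting control group". The control is an active programme of detoxification, counselling, a twelve-step programme and life-skills classes, and "individual sessions are also scheduled with psychologists once weekly".

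**The concern.** The two scales are attached only to contrasts over time. Both arms receive treatment and both may improve, so a significant pre/post change in the IICRA arm says nothing about whether IICRA does better than the control. Only the independent t-test can address that question, and its description leaves open what is compared, when, and on which score.

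The use of the pre-assessment matters more here than in a trial that mixes both arms within a site. Because each arm comes from its own clinic, nothing in the recruitment assures that starting scores are similar, and the SAP plans no baseline comparison. A t-test on post scores would discard the one measurement that could reveal or adjust for a difference. At stake are a possible false treatment effect, avoidable loss of precision, and a free choice among several tests after the data are in.

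**Working it through.** **What the wording allows.** There are 2 scales (SCL-90, ARQ), 3 sessions from discharge onward (discharge date, month 5, month 6) and 2 score types (post or change). That makes 2 × 3 × 2 = 12 different independent t-tests that fit the SAP sentence. The label for the time point is also unsettled: the SAP lists post assessment and follow-up separately, while the protocol counts the discharge-date session as the first follow-up.

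**Figures to reproduce.** The plan gives no effect size, SD, correlation or power for this comparison. The retention figures agree with each other: 28 control + 31 IICRA = 59 completers at the last follow-up, and 6 + 3 = 9 losses = 68 − 59.

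**Illustration of bias.** All inputs except the sample sizes are assumptions: baseline gap between clinics D = 0.5 SD, pre/post correlation r = 0.5, equal SDs (set to 1) and no arm effect. Positive means in the direction of the gap. Let G be the part of the clinic gap present at post. Then:

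- post-score difference: bias = G
- change-score difference: bias = G − D
- ANCOVA on the pre score: bias = G − rD

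| How the clinic gap evolves | G | Post-only | Change | ANCOVA |
|---|---|---|---|---|
| Acts only through the pre score | rD = 0.25 | +0.25 | −0.25 | 0 |
| Stable over time | D = 0.50 | +0.50 | 0 | +0.25 |
| Fades by post | 0 | 0 | −0.50 | −0.25 |

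Each estimator is unbiased in exactly one row.

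**False-positive rates at a nominal two-sided 5%.** With 28 and 31, h = 1/28 + 1/31 = 0.0680, so the standard error of a post-score difference is √0.0680 = 0.261. For a change score it is multiplied by √(2(1 − r)) = 1, so it is the same. A bias of 0.25 gives a noncentrality of 0.25/0.261 = 0.96 and rejection in 15.6% of trials. A bias of 0.50 gives 0.50/0.261 = 1.92 and 47.0% (noncentral t, 57 df). The ANCOVA rates come from simulation, which also reproduced the biases above:

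| Gap | Post-only | Change | ANCOVA |
|---|---|---|---|
| Through the pre score | 16% | 16% | 5% |
| Stable | 47% | 5% | 18% |
| Fades | 5% | 47% | 18% |

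Halving the gap to 0.25 SD brings the post-only rate down to 8% in the first row and 16% in the second.

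**Precision with no gap.** The variance of ANCOVA relative to post-only is 1 − r² = 1 − 0.25 = 0.750. Allowing for chance baseline differences, it is 0.750 × (1 + 1/(59 − 4)) = 0.764. The reduction is therefore about 24-25%.

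**The case against.** Five points can be made for the plan.

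- **The t-test plainly covers both scales.** That is a fair reading, but session, score type and use of the pre-assessment stay open.
- **A t-test on change scores is still an independent t-test.** This stands. A reader might infer that the SAP chose an unadjusted post-score test. The documents do not say so, and the bias figures for post scores apply only if that is what was done. The supported defect is that the test is unspecified.
- **Post scores are not always the worst choice.** This also stands. A reader might infer that a post-score test is biased whatever happens. If the clinic gap fades, it is the only unbiased estimate of the three, and both baseline-using estimates err in the same direction. The protocol has 21 days of detoxification before the intervention and 90-120 days of residence, and does not date the pre-assessment, so fading cannot be excluded.
- **The protocol calls the study randomized and the sites identical, or equal in structure, routine and staff.** These statements describe facilities, not patients' starting scores. They do caution against assuming that a gap exists, and none is claimed here.
- **The SAP's list may not be exhaustive.** It says that the important analyses include these three. The point is therefore limited to the one between-arm test that is listed.

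A reader might also infer from the 25% with comorbid illness that SCL-90 is to be compared only in that subset. The SAP states no such restriction, and all participants is the natural reading.

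**Conclusion.** The concern holds as a gap in specification with a practical consequence. The SAP does not determine how the comparative objective is answered, and the tests it ties to named scales cannot answer it. If post scores are compared without the pre-assessment, a 0.5 SD clinic gap would bias the result by 0 to 0.50 SD, depending on how the gap evolves. Even with no gap, about a quarter of the variance would be given up.

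The gap, the correlation of 0.5 and equal SDs are assumptions; the documents give none of them. The biases do not depend on sample size. The rejection rates use the 28 and 31 who completed the last follow-up, and numbers at discharge may be slightly higher.

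ANCOVA is the sensible main analysis for its precision and its use of a measured baseline, but it does not cure the design. No estimator is unbiased in all three scenarios, and none can separate the effect of IICRA from that of the clinic that delivered it.

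**What to change.** Amend the SAP as follows.

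1. For ARQ and for SCL-90, in all participants with data, compare the arms at one named post-baseline session by ANCOVA with the pre-assessment score of the same scale as covariate. Report the adjusted difference with a 95% CI. Make this the single main comparative analysis for each scale.
2. State which session the post assessment is, and reconcile the SAP's separate post and follow-up assessments with the protocol's count of the discharge session as the first follow-up.
3. Report pre-assessment scores by clinic.
4. Report the change-score and unadjusted post-score differences as sensitivity analyses. Say that each of the three estimates is unbiased only under its own assumption about how a clinic gap evolves, and that the documents cannot show which assumption holds.
5. Present the paired t-tests and the ANOVA over time as description only, with no conclusion of superiority.
6. State that adjustment cannot separate IICRA from clinic.

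The cost is SAP wording and a small extra analysis. No new data are needed, provided both scales were recorded at pre-assessment in both arms. The documents imply this (68 participants at pre-assessment) but do not state it. The SAP is in the past tense and the protocol already reports final retention, so if results have been seen, the re-analysis must be disclosed as post hoc.

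### The only SCL-90 analysis the SAP names is a within-person pre/post test, so no specified analysis answers the comparative or the six-month comorbidity question

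*SAP*

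**What the plan says.** The protocol raises comorbidity in two places. The first objective is comparative: whether IICRA has "better efficacy in treating substance dependence along with comorbidities than the indoor conventional treatment". Research Method and Design describes participants as "followed up for six months to check the effectiveness of IICRA in the context of relapse and recovery from SUD as well as from comorbidities". The visits were set out as follows: "first session was conducted on the discharge date from the facility, second was on fifth month and third was on sixth month following discharge".

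The SAP names three procedures.

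- **Independent t-test:** "Independent sample t-test was used to understand the efficacy of the treatment program between control and experimental groups". No outcome or visit is given.
- **Paired t-test:** "In order to assess the differences on pre and post assessment of interventions based on SCL-90 (scale of comorbidity". This is the only mention of SCL-90. The SAP does not date the post-assessment, and does not say whether the test is run in each arm or on the pooled sample.
- **One-way ANOVA:** "One way ANOVA was used to understand the differences between pre assessment, post assessment and follow up", in order to conclude about the "recovery of the participants which is measured by ARQ (Addiction recovery questionnaire". This is the only analysis that mentions follow-up, and it is tied to ARQ.

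**The concern.** A paired t-test asks whether the same people changed. It cannot show that one arm changed more than the other, which is what the first objective asks. Both sites treat residential patients and, according to the protocol, have the same length of stay, so symptom scores may fall in both arms for reasons unrelated to IICRA. A significant paired result in the IICRA arm, or a significant result in one arm and not in the other, would not support the comparative claim.

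The second gap is duration. Recovery from comorbidities is a stated reason for the six months of follow-up, yet no SCL-90 analysis is specified at any follow-up visit. A comorbidity conclusion could therefore be drawn from within-arm change over an undated pre/post interval. Alternatively, it could come from a between-arm test whose outcome and visit were chosen after the data were seen.

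**Working it through.** **1. Questions set against specified analyses**

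| Question in the protocol | SAP analysis that names SCL-90 | Does it answer? |
|---|---|---|
| IICRA v conventional treatment on comorbidities (Objectives) | Paired t-test, pre v post | No: there is no arm contrast |
| Recovery from comorbidities over six months (Research Method and Design) | None at a follow-up visit | No |

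The ANOVA sentence lists pre, post and follow-up as three separate levels, and the SCL-90 sentence uses only the first two. In the SAP's own vocabulary, post-assessment is therefore distinct from follow-up.

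**2. Why the paired test cannot stand in for the arm contrast**

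Suppose each arm has the same mean change, equal to c standard deviations of change. The paired statistic is t = c × √n. With the completers this is c × √28 = 5.29c in control and c × √31 = 5.57c in IICRA. Both grow with c, while the between-arm difference in change is zero whatever c is.

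**3. Numbers available at the last follow-up**

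Inputs are from the end of Research Method and Design.

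- Control: 34 − 3 − 1 − 2 = 28
- IICRA: 34 − 2 − 1 = 31
- Total: 28 + 31 = 59 of 68, which matches the protocol's figure
- Loss: 6/34 = 17.6% in control and 3/34 = 8.8% in IICRA

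**4. What a month-6 arm comparison could detect**

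The documents give no alpha, power or effect size. I assume two-sided alpha 0.05 and 80% power, and that every completer has a month-6 SCL-90 score.

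- Normal approximation: (1.960 + 0.842) × √(1/28 + 1/31) = 2.802 × 0.2607 = 0.73 SD
- With the t distribution: 0.743 SD
- Power at 28 v 31 (normal approximation): 48% at 0.5 SD, 63% at 0.6, 77% at 0.7 and 87% at 0.8
- Adjusted for the pre-assessment score, with assumed correlation r: 0.743 × √(1 − r²). For r = 0.3 this is 0.71 SD, for r = 0.5 it is 0.64 SD, and for r = 0.7 it is 0.53 SD.

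**5. The same comparison in those with comorbid illness**

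The protocol puts these at 25% of the sample: 0.25 × 59 = 14.75, or about 7.4 per arm if evenly split (assumed).

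- Normal approximation: 2.802 × √(2/7.375) = 1.46 SD
- With the t distribution: 1.58 SD

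**The case against.** The SAP introduces its procedures as the important ones and does not claim that the list is complete. Its independent t-test is for efficacy between the groups, and the first objective defines efficacy to include comorbidities. Read together, an arm comparison of SCL-90, even at month 6, may have been intended. This stands to the extent that a reader who infers that comorbidity was never compared between arms, or that no post-discharge evidence exists, goes further than the documents allow. They show only that no such test is specified. Leaving outcome and visit open does not close the gap, because the choice then falls to the analyst.

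A reader might also infer that the SCL-90 analysis stops on the day patients leave the residence. That is plausible but not established. The SAP does not date the post-assessment, and the protocol counts the discharge-date visit as the first follow-up session.

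Nor do the two documents contradict each other outright. The SAP is silent on SCL-90 after discharge, and neither document says whether the scale was collected at months 5 and 6. It is also unknown whether the pre-assessment preceded the 21-day detoxification, so early withdrawal recovery cannot be assumed to inflate the pre/post change.

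Two cautions apply to any remedy. The documents are written in the past tense and report final retention, so a new model is post hoc. IICRA patients came from one site and controls from the other, so an arm difference is also a site difference. Both stand and are carried into the fix.

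**Conclusion.** The point holds as a gap between questions and specified analyses. The one named SCL-90 test is within-person. It cannot support the comparative objective, and no SCL-90 analysis is specified for the follow-up that was meant to cover comorbidities. It should be corrected before any comorbidity conclusion is reported.

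The detectable differences describe the sensitivity of the replacement analysis and do not measure the defect. About 0.74 SD unadjusted, or 0.64 SD adjusted with r = 0.5, means that only fairly large average differences would be found reliably. At about 1.5 to 1.6 SD, the comorbid subgroup can say little. These figures rest on the assumed alpha, power and correlation, on complete month-6 scores among the 59 completers and, for the subgroup, on an even split between arms.

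**What to change.** - State when the post-assessment took place and at which visits SCL-90 was collected.
- Make the comorbidity analysis the between-arm difference in SCL-90, adjusted for the pre-assessment score, at post-assessment and, if the scale was collected then, at month 6. Fit one model, such as a mixed model, to all available scores, because loss was unequal between arms. Report estimates with confidence intervals.
- Keep the paired changes as description only.
- Label the analysis post hoc, since the data are already in hand, and state that arm is confounded with site. No adjustment for the pre-assessment score removes that confounding.
- If SCL-90 was not collected after discharge, remove the six-month comorbidity claim from the follow-up paragraph of Research Method and Design, and limit comorbidity conclusions to the pre/post period.

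The cost is SAP wording and one model, with no new data collection. The downside is a little more analysis work and a comorbidity conclusion that may be narrower or less favourable.
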